### 6.6.1. Dose Interruptions

The doses of INCB099280 and axitinib may be adjusted by dose interruptions with or without dose reductions of axitinib. Treatment interruptions for AEs associated with INCB099280 and axitinib are provided in [Table 11](#), [Table 12](#), [Table 13](#), and [Table 14](#). The criteria for dose interruptions are based on the severity of an AE. Treatment interruptions may occur independently for the 2 study drugs. Study treatment may also be interrupted for reasons other than treatment-related AEs (such as medical/surgical events or logistical reasons not related to study therapy).

In general, treatment may resume once the AE has improved to  $\leq$  Grade 1 unless there are other comorbidities or other circumstances present that would contraindicate the resumption of study treatment.

Treatment may be interrupted for up to 3 weeks (21 days), after which it should be discontinued. However, if further clinical benefit is anticipated with resumption of treatment, interruptions between 4 and 8 weeks may be considered in consultation/agreement with the sponsor.

### 6.6.2. Dose Reductions

Dose reductions of INCB099280 below 400 mg BID are not permitted.

Axitinib dose reductions (see [Table 9](#)) may be indicated based on individual safety and tolerability. If axitinib dose reduction from 5 mg BID is required, the next recommended dose level is 3 mg BID. If a further dose reduction is required, the next dose level will be 2 mg BID. Axitinib should be permanently discontinued if the participant cannot tolerate 2 mg BID.

**Table 9: Axitinib Dose-Reduction Scheme**

Initially Assigned Axitinib Dose	First Dose Reduction	Second Dose Reduction
5 mg BID	3 mg BID	2 mg BID
3 mg BID	2 mg BID	NA

Intraparticipant dose escalation is not permitted.

### 6.6.3. Criteria and Procedures for Dose Interruptions and Adjustments of Study Drug

Safety concerns should be discussed with the sponsor immediately upon occurrence or awareness to determine if the participant should continue or discontinue study treatment.

Treatment with INCB099280 and axitinib may be delayed up to 3 weeks (21 days) to allow for resolution of toxicity. Participants may resume treatment if no medical condition or other circumstance exists that, in the opinion of the investigator, would make the participant unsuitable for participation in the study. The treating investigator should contact the sponsor to discuss the case of a participant whose treatment has been delayed for more than 21 days before restarting treatment with INCB099280 or axitinib.

Management guidelines for AEs requiring dose modifications for INCB099280 and axitinib are described for general toxicities (see [Section 6.6.4](#)) and for irAEs (see [Section 6.6.5](#)). Participants requiring dose reduction of INCB099280 will be discontinued from INCB099280 treatment. Dose reductions of axitinib should be made following the dose-modification guidelines and

according to the clinical judgment of the investigator. Participants may resume treatment once the AE resolves to  $\leq$  Grade 1 or baseline if no medical condition or other circumstance exists that, in the opinion of the investigator, would make the participant unsuitable for further treatment and participation in the study.

#### 6.6.4. Management of Non-Immune-Related Adverse Events

The guidance presented in [Table 10](#) should be followed as best practice for decisions regarding management of non-irAEs.

**Table 10: Non-Immune-Related Adverse Event Management Guidelines for INCB099280**

CTCAE Grade	Suggested Modification for INCB099280
Grade 1 or Grade 2	Continue treatment at the discretion of the investigator.
Grade 3	Withhold treatment until resolution to $\leq$ Grade 1 or baseline. Restart INCB099280 at the same dose at the discretion of the investigator. Permanently discontinue study drug at the third occurrence unless approved by the medical monitor to continue.
Grade 4	Permanently discontinue study treatment or discuss with the medical monitor if a treatment algorithm for CTCAE Grade 3 events (above) is appropriate.

#### 6.6.5. Management of Immune-Related Adverse Events

An AE of a potential immunologic etiology or an irAE may be defined as an AE consistent with an immune phenomenon associated with drug exposure after all other etiologies have been eliminated. Immune-related AEs are expected based on the mechanism of action of INCB099280 and reported experience with other anti-PD-(L)1 agents. If an irAE is suspected, efforts should be made to rule out neoplastic, infectious, metabolic, autoimmune, toxic, or other etiologic causes before categorizing an AE as an irAE. Participants who develop a  $\geq$  Grade 2 irAE should be discussed immediately with the sponsor.

Continuation, withholding, or discontinuation of INCB099280 will depend on the severity of the irAE and affected organ/organ system and should be discussed with the medical monitor.

Participants should receive appropriate supportive care measures as deemed necessary by the treating investigator. Suggested measures for the management of irAEs for INCB099280 are outlined in [Table 11](#). For each AE, attempts should be made to rule out other causes, including but not limited to metastatic disease, bacterial infection, or viral infection that might require specific supportive care.

For additional management guidance for irAEs not detailed in the Protocol, or for details on diagnostic algorithms for an irAE if needed, refer to the ASCO, ESMO, or NCCN Clinical Practice Guidelines ([Haanen et al 2022](#), [NCCN 2021](#), [Schneider et al 2021](#)).

**Table 11: Management Guidelines for Immune-Related Adverse Events**

Severity (CTCAE v5 Grade)	INCB099280	Evaluation and Management
Pneumonitis		
Grade 1	
 
Withhold INCB099280 or continue with close monitoring.
 
Withhold INCB099280 for radiographic evidence of pneumonitis progression.
 
May resume with radiographic evidence of improvement or resolution if held.
 
	
 
Monitor as appropriate (CT, spirometry/DLCO, history and physical examination, pulse oximetry, chest x-ray).
 
If no improvement, treat as Grade 2.
 

Grade 2	Withhold INCB099280 until improvement to $\leq$ Grade 1.	
 
Administer systemic corticosteroid (prednisone 1-2 mg/kg or equivalent) with taper over 4-6 weeks.
 
Consider empirical antibiotics.
 
Consider bronchoscopy with bronchoalveolar lavage.
 
Monitor at least once per week (history and physical examination, pulse oximetry, consider radiologic imaging).
 
If no improvement within 2-3 days of treatment with prednisone, treat as Grade 3.
 
Consultation with pulmonary and infectious disease specialists as necessary.
 

Grade 3, Grade 4, or recurrent Grade 2	Permanently discontinue INCB099280.	
 
Administer IV methylprednisolone 1-2 mg/kg or equivalent with taper.
 
Consider empirical antibiotics.
 
If no improvement after 2 days, may add infliximab 5 mg/kg, IV mycophenolate mofetil 1 g twice daily, IV immune globulin for 5 days, or cyclophosphamide.
 
Consultation with pulmonary and infectious disease specialists if necessary.
 
Bronchoscopy with bronchoalveolar lavage and/or transbronchial biopsy.
 
 
Note: If clinical presentation is consistent with pneumonitis, transbronchial biopsy is not needed.

Diarrhea/colitis		
Grade 1	
 
Continue INCB099280 or hold INCB099280 temporarily.
 
Resume INCB099280 if toxicity does not exceed Grade 1 or resolves.
 
	
 
Closely monitor by telephone or electronic medical system for symptom changes every 3 days or more frequently if needed until stabilized.
 
Provide supportive care (hydration, electrolyte replacement, dietary changes).
 
May obtain consultation with a gastroenterology specialist for prolonged event and consider endoscopy with biopsies.
 

**Table 11: Management Guidelines for Immune-Related Adverse Events (Continued)**

Severity (CTCAE v5 Grade)	INCB099280	Evaluation and Management
Diarrhea/colitis (continued)		
Grade 2 or Grade 3	Withhold INCB099280 until improvement to ≤ Grade 1.	
Grade 2:
 
 
Consider consultation with a gastroenterology specialist.
 
Consider symptomatic treatment with an antidiarrheal agent if infection has been ruled out.
 
Administer systemic corticosteroids (prednisone 1 mg/kg or equivalent) until symptoms improve to Grade 1 and then taper over 4-6 weeks.
 
Consider infliximab or vedolizumab for steroid-refractory colitis (no decrease by 1 grade in 72 hours) or steroid-dependent colitis or colitis with high-risk features on initial endoscopy examination.
 
 
Grade 3:
 
 
Administer systemic corticosteroids (prednisone 1-2 mg/kg or equivalent) until symptoms improve to Grade 1 and then taper over 4-6 weeks.
 
Consider IV methylprednisolone.
 
Consider early introduction of infliximab or vedolizumab in addition to steroids in participants with high-risk endoscopic features or inadequate response to steroids.
 
Consider hospitalization for participants with dehydration or electrolyte imbalance.
 
Consultation with a gastroenterology specialist for additional workup as appropriate.
 

Grade 4 or recurrent Grade 3	Permanently discontinue INCB099280.	
 
Administer IV methylprednisolone 1-2 mg/kg or equivalent until symptoms resolve to Grade 1 and then taper over 4-6 weeks.
 
If no improvement after 3 days, consider infliximab or vedolizumab.
 
Consultation with a gastroenterology specialist for additional workup as appropriate.
 

Hepatitis (AST/ALT increased and/or total bilirubin increased)		
Grade 1	Continue INCB099280.	
 
Repeat laboratory measurements 1-2 times/week.
 
Consider alternate etiologies.
 
Provide supportive care for symptoms.
 

**Table 11: Management Guidelines for Immune-Related Adverse Events (Continued)**

Severity (CTCAE v5 Grade)	INCB099280	Evaluation and Management
Hepatitis (AST/ALT increased and/or total bilirubin increased) (continued)		
Grade 2	Withhold INCB099280 until improvement to $\leq$ Grade 1.	
 
Repeat laboratory measurements every 3 days until return to baseline.
 
If elevations persist after 3 days or symptomatic, administer systemic corticosteroids (prednisone 0.5-1 mg/kg or equivalent) with taper over at least 1 month when symptoms improve to <math>\leq</math> Grade 1.
 
If inadequate improvement over 3 days, consider adding mycophenolate mofetil if an infectious cause is ruled out.
 
Infliximab should NOT be used.
 

Grade 3	Permanently discontinue INCB099280.	
 
Repeat laboratory measurements every 1-2 days until return to baseline.
 
Administer IV methylprednisolone 1-2 mg/kg or equivalent with taper around 4-6 weeks when <math>\leq</math> Grade 1 with re-escalation as needed.
 
If corticosteroid refractory, consider liver biopsy and addition of azathioprine or mycophenolate mofetil.
 
Infliximab should NOT be used.
 
Consultation with a hepatology specialist for additional workup as appropriate.
 

Grade 4	Permanently discontinue INCB099280.	
 
Recommendations as above for Grade 3.
 
2 mg/kg/d methylprednisolone or equivalent.
 

Dermatitis		
Grade 1	Continue INCB099280.	Treat with topical emollients and/or mild- to moderate-potency topical steroids.
Grade 2	Consider holding INCB099280.	
 
Monitor weekly for improvement. If no improvement after 4 weeks, regrade toxicity as Grade 3.
 
Supportive care with topical emollients, oral antihistamines, and medium- to high-potency topical steroids.
 
Consider initiating prednisone 0.5-1 mg/kg or equivalent followed by tapering over 4 weeks. For participants with pruritus without rash, consider topical anti-itch remedies.
 

Grade 3	Withhold INCB099280 until improvement to $\leq$ Grade 1.	
 
Consultation with a dermatology specialist advised.
 
Administer IV methylprednisolone 1-2 mg/kg or equivalent with slow taper upon resolution.
 
Monitor for progression to severe cutaneous adverse reaction (eg, Stevens-Johnson syndrome, toxic epidermal necrolysis, drug reaction with eosinophilia and systemic symptoms/drug-induced hypersensitivity syndrome).
 

Grade 4 or recurrent Grade 3	Permanently discontinue INCB099280.	

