#### **4.1.3. Safety Monitoring**

During the conduct of Part 1 of the study, the sponsor will convene approximately biweekly telephone conferences with the investigative site staff to provide clinical updates on participants who remain on-study. Investigators who are unable to attend and have participants on-study will be requested to provide written updates prior to the meeting to keep all involved parties informed. An agenda will be provided in advance of these meetings, and minutes (including written summaries of cumulative participant-level safety and tolerability information, antitumor activity, and key discussion points and decisions) will be circulated to all investigative sites.

During Part 2 of the study, the sponsor monitoring of the study will include periodic DMC review. If any issues concerning participant safety arise during the study, this will be discussed at the investigator-sponsor meetings and, if appropriate, will be referred to the DMC.

Enrollment of participants into Part 2 may be suspended if > 40% of participants (when 5 or more participants have been enrolled) have an AE  $\geq$  Grade 3 that is attributable to the investigational agent (INCB099280) and that persists over 7 days despite adequate management.

See Section 5.7 for additional information on the Part 2 DMC.

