
 
<math>\geq 2</math> Grade ocular irAEs.
 
Grade 3 irAEs that do not improve to at least Grade 1 in <math>< 5</math> days with appropriate care or with corticosteroid therapy. Exception: Grade 3 or 4 endocrinopathy that is adequately controlled with hormone supplementation.
 
Grade 4 irAEs, regardless of duration.
 
Grade <math>\geq 2</math> myocarditis and/or pericarditis
 
Grade <math>\geq 2</math> myasthenia gravis, Guillain-Barré syndrome
 
Any grade encephalitis and/or demyelinating disease
 

General

Participant being unable to receive at least 75% (ie, 32 doses) of INCB099280 or axitinib doses during the DLT observation period because of treatment-related toxicity, even if the toxicity does not meet DLT criteria defined above.
 
Note: Exceptions include the DLT exclusions mentioned above.

MTD

 
In Part 1, the MTD will be defined as described in Section 4.1.1 and according to Table 5.
 
In Part 2, participants will be continually evaluated for safety, including AEs <math>\geq</math> Grade 3 that are attributable to the study treatment. If warranted, enrollment of participants may be suspended until the sponsor, investigators, and DMC have determined the appropriate course of action.
 

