### Assessment of Intensity

The severity of AEs will be assessed using CTCAE v5.0 Grades 1 through 5. If an event is not classified by CTCAE, the severity of the AE will be graded according to the scale below to estimate the grade of severity.

The investigator will make an assessment of intensity for each AE and SAE reported during the study and assign it to 1 of the following categories:

- **Grade 1:** Mild; asymptomatic or mild symptoms; clinical or diagnostic observations only; treatment not indicated.
- **Grade 2:** Moderate; minimal, local, or noninvasive treatment indicated; limiting age-appropriate activities of daily living.
- **Grade 3:** Severe or medically significant but not immediately life-threatening; hospitalization or prolongation of hospitalization indicated; disabling; limiting self-care activities of daily living.
- **Grade 4:** Life-threatening consequences; urgent treatment indicated.
- **Grade 5:** Fatal.

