#### Follow-Up of Adverse Events and Serious Adverse Events

- The investigator is obligated to perform or arrange for the conduct of supplemental measurements and/or evaluations as medically indicated or as requested by the sponsor to elucidate the nature and/or causality of the AE or SAE as fully as possible. This may include additional laboratory tests or investigations, histopathological examinations, or consultation with other health care professionals.
- Once an AE is detected, it should be followed in the Adverse Events Form in the eCRF until it has resolved or until it is judged to be permanent; assessment should be made at each visit (or more frequently if necessary) of any changes in severity, the suspected relationship to the study treatment, the interventions required to treat the event, and the outcome.
- When the severity of an AE changes over time for a reporting period (eg, between visits), each change in severity will be reported as a separate AE.
- Updated SAE information will be recorded in the originally completed eCRF and reported to Incyte Pharmacovigilance (in the SAE EDC CRF) until resolution, stabilization, the event is otherwise explained, or the participant is lost to follow-up.
- Any updated SAE data (including SAEs being downgraded to nonserious) will be submitted to the sponsor (or designee) within 24 hours of receipt of the information.

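### The dermatitis row of Table 11 changes a Grade 2 event to Grade 3 on duration alone, contrary to the CTCAE v5.0 rules for recording, DLT grading and analysis, and so can inflate the Grade 3+ TEAE counts

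*Protocol*

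**What the plan says.** The Grade 2 dermatitis row of Table 11 (Section 6.6.5) reads: "Monitor weekly for improvement. If no improvement after 4 weeks, regrade toxicity as Grade 3". The table's first column is headed as the CTCAE v5 severity grade. Section 6.6.5 introduces the table as guidance: "Suggested measures for the management of irAEs for INCB099280 are outlined in" Table 11.

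The grading rules are elsewhere in the protocol:
- Section 9.3, Assessment of Intensity: "The severity of AEs will be assessed using CTCAE v5.0 Grades 1 through 5". The fallback scale for events that CTCAE does not classify defines Grade 3 by severity and function, with no duration element.
- Section 6.5: the investigator grades DLTs by CTCAE v5.0.
- Section 10.4.2.1: the AE analysis uses NCI CTCAE v5.0 grades and tabulates Grade 3 or higher TEAEs, overall and treatment-related.
- Section 9.3, Follow-Up: when severity changes over time, "each change in severity will be reported as a separate AE".

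For a comparable step, the pneumonitis rows of Table 11 escalate the handling and leave the grade alone: "If no improvement, treat as Grade 2" in the Grade 1 row and "If no improvement within 2-3 days of treatment with prednisone, treat as Grade 3" in the Grade 2 row.

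**The concern.** A grade is meant to measure severity. The dermatitis row makes it measure elapsed time, for one event type, at those sites that read the row as a grading instruction. Because the table presents its grades as CTCAE v5 grades, that reading is natural, and nothing in the protocol says that the regrade stays out of the eCRF.

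At stake are the Grade 3+ TEAE and treatment-related Grade 3+ TEAE tabulations and their consistency across sites. Two decision points also use Grade 3 events. One is the review of DLTs after Day 21, before the RDE is set (Section 6.5 with Table 8). The other is the Part 2 suspension rule in Section 4.1.3.

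**Working it through.** The protocol gives no figure to reproduce here. The check is mainly a comparison of passages, with arithmetic only for the size.

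**1. Do the rules conflict?** Take a Grade 2 dermatitis that is unchanged at 4 weeks. Under Sections 6.5, 9.3 and 10.4.2.1 its grade is whatever CTCAE v5.0 gives. Under Table 11 it becomes Grade 3 because 4 weeks have passed. The two give different grades for the same event. Table 11 does not need this device: pneumonitis uses treat-as wording, and persistent Grade 2 renal events and persistent Grade 2 events under other irAEs are placed in the Grade 3 management row without being regraded.

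**2. Where could a regraded record go?** If entered, it is a new Grade 3 AE under Section 9.3.
- *Grade 3+ TEAE tables (10.4.2.1):* counted. Also counted in the treatment-related table if related.
- *Overall irAE tabulation (10.4.2.1):* unchanged. It has no grade cut, so the event is already in it at Grade 2.
- *21-day DLT rate and Table 5 decisions:* unchanged. 4 × 7 = 28 days, which exceeds the 21-day window, so the regrade of a dermatitis that began on treatment falls outside it.
- *Late-DLT review (6.5, Table 8):* possible. Table 8 lists "Grade 3 irAEs that do not improve to at least Grade 1 in" fewer than 5 days, and Section 6.5 considers later DLTs before the RDE is set.
- *Part 2 suspension (4.1.3):* possible only if the event is "attributable to the investigational agent (INCB099280) and that persists over 7 days despite adequate management".

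**3. How many participants?** The protocol gives no dermatitis rate. Assume Grade 2 dermatitis in 5% to 15% of participants, with 10% to 30% of those not improving in 4 weeks.
- Low: 0.05 × 0.10 = 0.5%; × 132 = 0.66 participants.
- High: 0.15 × 0.30 = 4.5%; × 132 = 5.94 participants.
- Part 1, about 12 participants: 12 × 0.005 = 0.06 to 12 × 0.045 = 0.54.

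**4. Effect on the suspension rule.** The smallest counts strictly above 40% are 3 of 5, 5 of 10, 9 of 20 and 13 of 30; one fewer is exactly 40% and does not trigger. The probability of reaching the threshold x is the binomial tail P(X ≥ x) with rate q + d, where q is an assumed true qualifying rate and d is the added share of participants who qualify only through a regrade.

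| n | q | d = 0 | d = 1 point | d = 5 points |
|---|---|---|---|---|
| 5 | 20% | 5.8% | 6.6% | 10.4% |
| 30 | 20% | 0.3% | 0.5% | 2.2% |
| 30 | 30% | 8.4% | 10.5% | 22.0% |

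These figures let every regraded participant also satisfy the attribution and persistence conditions, so for the assumed q and d they lean high.

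**The case against.** The strongest reply is that Table 11 is suggested management, the sentence sits in the evaluation and management column, and no passage makes it an eCRF rule. Recording, DLT grading and analysis each name CTCAE v5.0, so false Grade 3 events arise only where a site lets a management table override all three. This stands as far as it goes: entry into the data is a risk and not a certainty. It does not remove the contradiction, because the protocol never says which instruction prevails.

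A reader might infer more than the documents support:
- *That the primary or secondary endpoints are biased.* Table 4 and Table 23 name DLTs and TEAE incidence (with TEAEs leading to dosing modification in Table 4). None is defined as a Grade 3+ rate.
- *That the irAE rate or the dose-finding decisions are distorted.* Step 2 of the working shows that they are not.
- *That a regraded event automatically meets the persistence conditions because it has already lasted 4 weeks.* What lasted 4 weeks is the Grade 2 event. Table 8 and Section 4.1.3 concern how a Grade 3 event behaves under appropriate care or adequate management, and on the literal reading Grade 3 begins at the regrade.
- *That one false event would halt Part 2.* The rule says enrollment may be suspended, and attribution to INCB099280 is required.

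The objection to the size also has force. Any rule set at more than 40% has boundary counts. The 15% upper assumption may be generous: the list in Section 2.3.2 of TEAEs seen in at least 15% of participants on axitinib plus pembrolizumab contains no rash or dermatitis term, although that is a different combination.

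**Conclusion.** The point holds as a contradiction in the grading rules with a limited reach. A site that follows the dermatitis row literally creates a Grade 3 record for an event whose severity did not change. That can inflate the Grade 3+ and treatment-related Grade 3+ TEAE tabulations and lead to uneven grading across sites. It may also be considered in the judgement-based late-DLT review and, if attributed to INCB099280 and persistent over 7 days despite adequate management, in the discretionary suspension count.

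The size is probably small: about 0.7 to 6 of 132 participants if every such event were regraded and entered. That range rests wholly on the assumed rates, since the protocol supplies none. The contradiction itself rests on no assumption. The point merits correction because the remedy is cheap, not because the effect is large.

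**What to change.** Reconcile the Grade 2 dermatitis row of Table 11 with Sections 6.5, 9.3 and 10.4.2.1. State that the grade entered in the eCRF and used in the safety tables, the DLT review and the Section 4.1.3 count is the CTCAE v5.0 grade, and that time without improvement does not by itself change it. Carry the same sentence into the eCRF completion guidelines.

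The row immediately below covers Grade 3 dermatitis, and the next covers Grade 4 or recurrent Grade 3, where INCB099280 is permanently discontinued. Whether a regraded event is meant to count as a Grade 3 occurrence for those rows is unclear. The sponsor should reconcile that wording at the same time; no management rule is proposed here.

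Cost: one sentence in the protocol and one in the eCRF guidelines, with no extra data collection.
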